### Acute Leukemia Patients

		DL3A	DL3B	DL4A	DL4B	DL5A	DL5B	DL6	Exp. (80mg QD) 14-21	Exp. (80mg QD) 14-21	
DL1 (10mg	DL2 (20mg	(40mg QD)	(20mg BID)	(80mg QD)	(40mg BID)	(120mg	(120mg	(160mg	– AML/de	_	
QD) 14-21	QD) 14-21	14-21	21-21	14-21	14-21	QD) 14-21	QD) 21-21	QD) 14-21	novo	AML/MDS	Total
(N=3)	(N=3)	(N=4)	(N=3)	(N=4)	(N=8)	(N=7)	(N=6)	(N=7)	(N=19)	(N=16)	(N=80)

### **Other Hematologic Malignancies Patients**

			DL4A	DL4B	DL5A	DL5B	DL5C	DL5D	Exp. (80mg	
DL1 (10mg	DL2 (20mg	DL3 (40mg	(80mg QD)	(40mg BID)	(120mg QD)	(120mg QD)	(120mg QD)	(120mg QD)	QD) 14-21 -	
QD) 21-21	QD) 21-21	QD) 21-21	21-21	21-21	21-21	14-21	5-7	7-21	DLBCL	Total
(N=5)	(N=3)	(N=4)	(N=7)	(N=6)	(N=7)	(N=3)	(N=5)	(N=5)	(N=16)	(N=61)

All analyses will be repeated in the two populations, AL patients and OHM patients, unless otherwise specified.

### 6.2 HANDLING OF MISSING DATA

In the event of a missing date, replacement will be applied so as to be in the worst case scenario, as follows:

### For the concomitant medication start date:

Completely missing dates will be estimated as the first treatment administration date.

If the day and the month are missing:

- If the year is the same as the year of the first treatment administration date, the date will be estimated as the first treatment administration date.
- If the year is different to the year of the first treatment administration date, the date will be estimated as the 1st January.

If only the day is missing:

- If the month/year are the same as the month/year of the first treatment administration date, the date will be estimated as the first treatment administration date.
- If the month/year are different from the month/year of the first treatment administration date, the date will be estimated as the first day of the month.

For the concomitant medication end date (if ongoing is not ticked at the end of the study):

Completely missing dates will be estimated by the End of Study date.

If the day and the month are missing:

- If the year is the same as the year of the End of Study date, the date will be estimated as the End of Study date.
- If the year is prior to the year of End of Study date, the date will be estimated as the 31 December.

If only the day is missing:

- If the month/year are the same as the month/year of End of Study date, the date will be estimated as the End of Study date.
- If the year or month is different to the year or month of End of Study date, the date will be estimated as the last day of the month.

If after imputation, the end date is before the estimation start date, the estimation start date will be replaced by the end date.

### For the start date of an adverse event:

Completely missing dates will be estimated as the first treatment administration date.

# 7. NUMBER OF PATIENTS

A total number of 141 patients were enrolled according to the number of observed DLs and expansion groups selected.

# 8. POPULATIONS

Enrolled Population: all patients who signed an Informed Consent Form.

Treated/Safety Population: all included patients receiving at least one dose of the investigational drug.

**Evaluable for Efficacy Population:** All treated patients with at least one available tumor assessment (BM aspiration for AL patients or imaging for OHM patients) by the end of cycle 2 or later, OR with earlier evidence (i.e. cycle 1) of response or progression.

**Evaluable for DLT Population:** all treated patients receiving at least 85% of the intended OTX015/MK-8628 dose during the first cycle (i.e.  $\geq$  12 days at full dose for AL and  $\geq$  18 days at full dose for other hematologic malignancies)\*, as well as patients not fulfilling these conditions, but who experienced DLT.

\*e.g. for DL1 (10 mg/day), AL patients receiving  $\geq$  120 mg over the first 21 days (10 mg x 12), or other hematologic malignancy patients receiving  $\geq$  180 mg over the first 21 days (10 mg x 18).

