- If one out of 3 patients of a cohort experiences a DLT during the first cycle (i.e. the first 21 days following study treatment initiation, regardless of the treatment schedule), 3 additional patients will be entered at this DL. If no more than 1/6 treated and evaluable patient experience a DLT, the dose escalation will proceed to the DL immediately above. As soon as a DLT is observed, the magnitude of dose escalation will follow a Fibonacci-like model (see below). If more than one patient out of 6 (or more than one out of 3) experiences a DLT, the DL will be considered exceeding the maximum tolerated dose (MTD) for this subset.
- Patients not evaluable for DLT (i.e. those having received less than 85% of the intended cumulative dose during the first 21 days) and who have not experienced a DLT, will be replaced.
- The dose escalation will be stopped independently in each subset upon decision of the Safety Monitoring Committee (SMC). This decision could be taken if one of the following conditions is met:
 - A DL exceeding the MTD has been reached
 - Biological activity (PD) or sustained biologically active concentrations (PK) of OTX015/MK-8628 have been achieved
 - Or any other unforeseen condition, which, in the judgment of the SMC, would prevent, or would not deserve, further dose escalation.
- In the absence of other data (PD or PK) suggesting a lower RD, the MTD will be considered the RD. At least 6 evaluable patients will be enrolled at the supposed RD (one DL below the dose exceeding the MTD) in each subset. The RD will be confirmed for each subset if no more than 1/6 patient experiences a DLT. Otherwise the DL immediately below will be explored with a minimum of 6 evaluable patients.

Expansion part

• Once the RD will be established with at least 3 patients having received at least 2 cycles of study treatment for each subset, the study will be prolonged with expansion cohorts in selected patients to confirm feasibility, safety, PK and PD at the RD. At least 12 evaluable patients with acute leukemia will be treated at the RD established for patients with acute leukemia. At least 12 evaluable patients with diffuse large B-cell lymphoma (DLBCL) or multiple myeloma (MM) will be treated at the RD established for patients. Additional expansion cohorts may be decided by the SMC, based upon the data collected during the dose escalation phase.

Inclusion criteria

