3.1.1 Dose escalation part

- Two dose escalation subsets will be assessed independently in parallel: patients with acute leukemia and patients with other hematological malignancies.
- Patients will be enrolled by successive cohorts of 3 patients in each dose escalation subset.
- Three patients will be initially treated at the starting dose level (DL) in each subset. If no dose limiting toxicity (DLT) is observed among these 3 patients during the first cycle of treatment (i.e. the first 21 days following study treatment initiation, regardless of the treatment schedule), the next 3 patients will be treated at the DL immediately above, according to the dose escalation schedule defined in section 5.2.4.1. In the absence of DLT observed at the completed DL, the dose will be doubled.

- At each DL in each subset, the second patient enrolled will not start the study treatment before the first treated patient of the cohort will have completed at least 2 weeks of treatment (i.e. 14 consecutive daily administrations). The first patient enrolled in a higher DL cohort will not start the study treatment before the last treated patient in the DL immediately below will have completed at least one cycle of study treatment (i.e. 21 days following study treatment initiation, regardless of the treatment schedule)..
- If one out of 3 patients of a cohort experiences a DLT during the first cycle (i.e. 21 days following study treatment initiation, regardless of the treatment schedule), 3 additional patients will be entered at this DL. If no more than 1/6 treated and evaluable patient experience a DLT, the dose escalation will proceed to the DL immediately above. As soon as a DLT is observed, the magnitude of dose escalation will follow a Fibonacci-like model. (see section 5.2.4.1).
- If more than one patient out of 6 (or more than one out of 3) patients experiences a DLT, the DL will be considered exceeding the maximum tolerated dose (MTD) for this subset.
- Patients not evaluable for DLT are those having received less than 85% of the intended cumulative dose during the first 21 days (i.e. those receiving less than 18 days of treatment for the continuous, 21-day schedule or less than 12 days of treatment for the intermittent, 14 days ON/ 7 days OFF schedule) and who have not experienced a DLT, will be replaced.

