11.2 ANALYSIS POPULATIONS

- Intent-to-treat population: all enrolled patients
- **Per protocol population**.: all enrolled patients with no violation of inclusion/exclusion criteria
- Evaluable for safety population: all patients having received at least one dose of OTX015
- Evaluable for DLT population: all treated patients having received at least 85% of the intended dose during the first cycle (i.e. ≥ 12 days at full dose for AL and ≥ 18 days at full dose for other hematological malignancies)* of OTX015/MK-8628 treatment, as well as patients not fulfilling these conditions, but having experienced a DLT.

*e.g. for DL1 (10 mg/day), patients with AL having received \geq 120 mg over the first 21 days (10 mg x 12), or patients with other hematological malignancies having received \geq 180 mg over the first 21 days (10 mg x 18).

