# 6. STATISTICAL METHODOLOGY

# 6.1 GENERAL CONSIDERATIONS

The statistical analysis will be performed by eXYSTAT, under the responsibility of the Sponsor OncoEthix GmbH and the study CRO, OTD, on the basis of the present document.

The statistical analysis will be performed using SAS® software, version 9.4 in a Windows XP operating system environment.

The baseline value is defined as the last available value prior to administration of the investigational product.

The study treatment phase is defined as the period between the date of first administration of investigational product and the date of last administration of investigational product + 30 days.

No replacement of missing values is planned, other than those noted in Section 6.2. Thus the number of patients included in the analyses may vary depending on availability of the parameter considered.

Descriptive statistics will be provided by dose level (DL1 to DL5 or DL6 then expansion cohort, depending on the disease cohort) and overall for each of the two patient cohorts (AL and OHM), and by time point when appropriate, according to the nature of the variable.

- For quantitative variables, descriptive statistics will include: number of missing values, number of observed values, minimum, maximum and median or mean and standard deviation.

- For qualitative variables, descriptive statistics will include: number and percentage of missing values, number of observed values, frequencies and percentages (only for the overall column) per modality.

Calculated statistics and percentages will be displayed with one decimal, unless otherwise specified.

No statistical tests will be performed due to the descriptive nature of this analysis.

In terms of terminology, the mention of "by dose level and overall" will always correspond to the following, according to the cohort:

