# **12. SAFETY EVALUATION**

# **12.1** SAFETY VARIABLES

Safety analyses will be performed in the Safety Population other than for DLT which will be presented in the evaluable for DLT population. All safety data from the study treatment phase will be presented.

Safety data are obtained from clinical and physical examinations, as well as vital signs evaluation.

TEAEs / signs and symptoms of disease observed by the investigator (preferably by the same physician for the same patient) or reported by patients to the study nurses will be recorded and graded according to NCI-CTCAE version 4.03.

Clinically significant laboratory results are those which have clinical consequences. The seriousness, the action taken regarding study medication and patient participation in the study, relation to study medication and the most likely cause, should then be recorded.

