# **12.3 PRIMARY CRITERION: DOSE LIMITING TOXICITY**

DLTs are defined as any treatment-emergent adverse events (TEAEs) occurring during the first cycle (i.e., the first 21 days following study treatment initiation; note that hypocellular bone marrow and no marrow blasts in AL patients had to be confirmed at day 43), leading to treatment interruption or dose adjustment, or any unforeseen drug-related AE leading to study treatment interruption or discontinuation, unless a relationship to study medication can be definitively ruled out.

The number of patients evaluable for DLT/with DLT in cycle 1 will be tabulated per dose level and overall for safety population.

Type of DLT will be tabulated for patients evaluable for DLT by DL and overall.

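### SAP 8 counts dosing days by disease, not schedule, for DLT evaluability; the counts misfit 29 of 61 OHM and 9 of 80 AL patients

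*SAP*

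**What the plan says.** SAP 8 opens the definition with "all treated patients receiving at least 85% of the intended OTX015/MK-8628 dose during the first cycle". An i.e. clause then turns this into at least 12 full-dose days for AL and at least "18 days at full dose for other hematologic malignancies". The only other way into the set is to have had a DLT. Protocol 11.2 has the same structure and the same disease-based count ("18 days at full dose for other hematological malignancies").

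Other places state the rule differently. Both synopses (dose escalation part) describe non-evaluable patients as "those having received less than 85% of the intended cumulative dose during the first 21 days", with no day counts. Protocol 3.1.1 and Protocol 9 do give day counts but attach them to the schedule: "those receiving less than 18 days of treatment for the continuous, 21-day schedule or less than 12 days of treatment for the intermittent".

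On use of the set, SAP 12.1 says "Safety analyses will be performed in the Safety Population other than for DLT which will be presented in the evaluable for DLT population". SAP 12.3 plans two tables. For the first, "The number of patients evaluable for DLT/with DLT in cycle 1 will be tabulated per dose level and overall for safety population"; the second gives type of DLT in the evaluable set. For categorical variables SAP 6.1 asks for "frequencies and percentages (only for the overall column) per modality".

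**The concern.** The two halves of the SAP 8 sentence are offered as equivalent, but the second fits only the schedules each disease group started on. The SAP 6.1 headers show that schedule later stopped following disease.

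If the day counts are programmed, an OHM patient planned for 14 or fewer dosing days in cycle 1 can never qualify on exposure. A fully dosed patient without a DLT is excluded and one with a DLT is included, so the denominator for the primary endpoint is selected on the outcome. In the OHM expansion column, the only OHM column at the recommended dose and schedule (80 mg once daily, 14-21), the evaluable count would equal the number of patients with a DLT. For AL patients on continuous dosing the error runs the other way: an under-dosed patient would count as evaluable.

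**Working it through.** **Inputs.** The 85% threshold and the 12 and 18 day counts come from SAP 8. Dose, schedule and N by column come from the SAP 6.1 headers. The SAP synopsis (expansion part) shows that 14-21 means dosing on days 1 to 14 of a 21-day cycle. I read 7-21 as 7 dosing days in 21 and 21-21 as continuous. The SAP does not define 5-7, so I tried two readings: 15 dosing days in 21 (5 on in every 7) and 10 in 21.

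**The plan's own figures reproduce for two schedules.**
- 14 days: 0.85 × 14 = 11.9, so 12.
- 21 days: 0.85 × 21 = 17.85, so 18.
- DL1 footnote: 0.85 × 140 mg = 119 mg and 0.85 × 210 mg = 178.5 mg. In 10 mg doses these become 120 mg and 180 mg, as printed.

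**Patients on other schedules.**
- AL total: 3+3+4+3+4+8+7+6+7+19+16 = 80. On 21-21: DL3B 3 + DL5B 6 = 9 (11.3%).
- OHM total: 5+3+4+7+6+7+3+5+5+16 = 61. Not on 21-21: DL5B 3 + DL5C 5 + DL5D 5 + expansion 16 = 29 (47.5%).
- Together: 38 of 141 (27.0%).

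**Day rule against the 85% cut, in mg over cycle 1.** Planned = daily dose × planned days; cut = 0.85 × planned; day rule = daily dose × 18 (OHM) or × 12 (AL).

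| Column | N | Planned | 85% cut | Day rule | Day rule / planned |
|---|---|---|---|---|---|
| OHM DL5B, 120 mg 14-21 | 3 | 1680 | 1428 | 2160 | 128.6% |
| OHM DL5C, 120 mg 5-7 (15 days) | 5 | 1800 | 1530 | 2160 | 120% |
| OHM DL5C, 120 mg 5-7 (10 days) | same 5 | 1200 | 1020 | 2160 | 180% |
| OHM DL5D, 120 mg 7-21 | 5 | 840 | 714 | 2160 | 257.1% |
| OHM expansion, 80 mg 14-21 | 16 | 1120 | 952 | 1440 | 128.6% |
| AL DL3B, 20 mg BID 21-21 | 3 | 840 | 714 | 480 | 57.1% |
| AL DL5B, 120 mg 21-21 | 6 | 2520 | 2142 | 1440 | 57.1% |

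Every OHM row needs more than the full planned dose, so none of the 29 can qualify on exposure. OHM patients able to be evaluable without a DLT number at most 61 − 29 = 32 under the day rule and 61 under the 85% rule. The 9 AL patients are affected only if they had 12 to 17 full-dose days and no DLT.

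**Illustration of the OHM overall percentage.** Assume all 61 were fully dosed, with 2 DLTs among the 32 on 21-21 and k among the 29. These DLT counts are invented to show scale. The 85% rule gives (2+k)/61 and the day rule (2+k)/(32+k).
- k = 1: 3/61 = 4.9% against 3/33 = 9.1%.
- k = 4: 6/61 = 9.8% against 6/36 = 16.7%.

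**The case against.** The strongest reply is that the 85% wording is the operative rule and the day counts are only a gloss that was right for DL1. Both synopses and Protocol 3.1.1 and 9 support that reading, and it is probably what was meant. A programmer would have to demand 129% to 257% of the planned dose under a rule headed 85%. This makes the worst case less likely. It does not settle the matter: the two sections that formally define the population both carry the disease-based counts, and nothing says which half prevails.

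Second, little depends on it. The study is complete, no tests are planned, the recommended dose was set by the SMC, and the DLT numerator is the same either way. The first SAP 12.3 table and the DLT shells in the SAP appendix are labelled safety population, so a DLT count on all treated patients is reported regardless. All of this stands, and it limits the damage to the evaluable counts and the OHM overall percentage.

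Third, validation by a second statistician (SAP 5), the dry runs and Listing i-2 could expose an emptied cohort. They could, but none supplies the rule to validate against, and the AL error would be less visible because it adds patients.

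Fourth, Listing i-2 allows for patients for whom DLT evaluation is not applicable. If expansion patients were so classed, 16 of the 29 would drop out, leaving 13. The SAP never says who is in that category, while SAP 5 and SAP 8 cover all treated patients, expansion included.

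**Conclusion.** The concern holds. SAP 8, like Protocol 11.2, gives the primary-endpoint population two definitions that disagree for the schedules of 38 of 141 patients. For 29 OHM patients the day count is unreachable and makes membership depend on the outcome; for 9 AL patients it is too lenient. The count of 29 would fall only if 5-7 or 7-21 meant 18 or more dosing days in cycle 1.

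How many patients would in fact change status cannot be told from the documents. The cohort columns would show wrong evaluable counts, and the OHM overall column a wrong percentage. The recommended dose is not called into question. This should be fixed before the DLT tables are final, but it does not threaten the trial's main conclusion.

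**What to change.** In SAP 8, delete the disease-based day counts and define the set as:

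> Treated patients whose cumulative cycle 1 dose in mg was at least 85% of the dose planned for their assigned dose level and schedule, plus any treated patient with a DLT.

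Milligrams are safer than full-dose days. As an arithmetic example on the 80 mg 14-21 schedule, 11 × 80 + 3 × 60 = 1060 mg is 94.6% of the planned 1120 mg and above the 952 mg cut, yet it contains fewer than 12 full-dose days.

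Keep the footnote, labelled as applying to the DL1 schedules only (AL 14-21, OHM 21-21). State what 5-7 meant as given, so that its planned cycle 1 dose is fixed. Derive or check the evaluability flag on this basis before the DLT tables are final, and record in SAP 14 the departure from the day counts in Protocol 11.2.

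The cost is one sentence, a footnote label, one definition, one line in SAP 14 and one flag to check or re-derive. No new data are needed.

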# 8.1 DATA SETS ANALYZED

Statistical analyses will be carried out as described below. The number of patients per analysis set will be tabulated by DL and overall according to the population evaluated.

A listing will also be provided (for CSR appendices).

The following table describes use of the above-defined patients populations in the different analyses conducted.

Analyses Sets	Enrolled	Safety	Evaluable for efficacy population	Evaluable for DLT
Disposition	×			
Population characteristics		$\checkmark$		
Compliance and exposure		$\checkmark$		
Efficacy assessments			✓	
DLT				✓
Safety assessment		$\checkmark$		

# 9. PATIENT DISPOSITION AND PROTOCOL DEVIATIONS

# 9.1 **PROTOCOL DISPOSITION**

The number of patients per center will be tabulated for enrolled, treated, evaluable for DLT and evaluable for safety patients will be detailed by DL and overall.

Reasons for discontinuation will be tabulated by DL and overall, and detailed in a patient listing for the CSR appendices. Patients classified by the investigator as reason="Other" but with evidence of clinical or tumoral progression will be reclassified as progression in the table.

Overview of treated conditions will be tabulated by AL (AML/ALL) or OHM (lymphoma, multiple myeloma, other).

# 9.2 **PROTOCOL DEVIATIONS**

Totals of major/minor protocol deviations, the number of patients with at least one major/minor protocol deviation and type of major/minor deviation will be tabulated for the enrolled population.

A listing of patients with protocol deviations for relevant items will be presented in the CSR Appendices.

Protocol deviations will be examined prior to database lock relative to inclusion and exclusion criteria and to protocol compliance with regard to administration of treatment and prohibited medication.

Major protocol deviations are defined as deviations liable to prevent or change the interpretation of the results of the study.

# **10. DEMOGRAPHICS AND OTHER BASELINE CHARACTERISTICS**

Demographic and other baseline characteristics recorded at the baseline visit (Day 0) before the first product administration will be described by DL and overall for the safety population.

# **10.1 DEMOGRAPHICS**

- Age (years; by category) and gender.
- ECOG performance status at the screening visit by score (0, 1, 2, 3, 4)
- Height (cm), weight (kg), BMI (kg/m^2) = weight in kg/(height in m) and BSA (m^2) = (W 0.425 x H 0.725) x 0.007184.
- Pregnancy test (positive, negative, NA)

# **10.2 DISEASE CHARACTERISTICS**

- Acute leukemia: Disease duration (months; = [screening year diagnosis year] \*12 + [screening month diagnosis month]), number of lines (in total=number of lines + number of NA in CRF page 17), number of lines prior therapy (from CRF page 17), type of systemic therapy (standard, AZA, aSCT, other: coded from CRF), leukemia WHO 2008 Classification, FAB classification, genetic group, bone marrow (from CRF page 401) (absolute value and 5-20%/>20%), presence peripheral blasts, hyperleukocytis (absolute value and >15\*10^9/l, hydroxyurea requirement (coded from prior medication), type (de novo/secondary/therapy related/ALL), cellularity (poor, intermediate, rich), extramedullary disease, cytogenetics and molecular genetics (from CRF page 15).
- For lymphoma: disease duration (months), number of lines in total (=number of lines + number of NA in CRF page 17), number of lines prior therapy (from CRF page 17), prior therapy (systemic, surgery, radiotherapy), type of systemic therapy (CHOP/R-CHOP, ASCT, other; coded from CRF), lymphoma

WHO 2008 classification, number of tumor sites (from CRF page 21), number of nodal sites, number of extranodal sites, BM involved (CRF pages 19 and 301).

 Multiple myeloma: disease duration (months), M-component (IgG, IgA, Bence Jones, Other), Kappa or Lambda light chain (max of the two values from CRF page 201), bone lesions, extramedullary disease, bone marrow plasma cells, cellularity (poor, intermediate, rich), prior therapy (systemic, surgery, radiotherapy), type of systemic therapy (alkylating, steroid, bortezomib, IMiD, ASCT, other; coded from CRF), number of lines prior therapy (from CRF page 17)

Listings of disease characteristics and cancer treatments will be provided for the CSR Appendices.

